Protocol

1. Title:

Assessing Efficacy of Intramuscular Promethazine for the Treatment of Intrathecal Morphine Induced Pruritus

Version 2.0

Date April 22, 20225

2. Investigators

Principal Investigator: [name]

Co-Investigators: [name]
[name]
[name]
[name] [name]
[name]
[name], MA

Study Coordinators: [name]

3. Abstract:

This study aims to analyze a novel approach for prophylaxis against pruritis caused by neuraxial narcotics. Neuraxial narcotics are commonly used in obstetric patients for cesarean delivery to help with pain control over the first 24 hours after the surgery. Slappendel demonstrated intramuscular promethazine (IMP) was an effective treatment for intrathecal morphine induced pruritis (ITMIP).¹ No other studies evaluated IMP for treatment of ITMIP. The primary aim of this study will be to evaluate effectiveness of IMP prophylaxis of ITMIP. Finding a prophylaxis for ITMIP other than naloxone, will allow for increased use of intrathecal narcotics and potentially decrease the use of systemic opioids in the initial post-operative period.

This study will use in-patients undergoing cesarean delivery at UF Health Shands Hospital in Gainesville, Florida.

4. Background and Significance:

Intrathecal morphine given during cesarean deliveries is one of the many ways providers currently help post-partum women with pain control. One major downside of intrathecal morphine is pruritus that occurs over the next 24-48 hours. During this time the mother should be enjoying time with her new infant, but instead is having to deal with the itching from the pain reliever we have given her. The

cause for the pruritus is not well known, but what is known is that anti-histamines such as diphenhydramine do not work. One class of medications known to help decrease ITMIP include mu opioid antagonists such as naloxone but some suggest there may be decreased analgesia when mu opioid antagonists are utilized. Further, due to the short half-life of naloxone, infusions of the medication must be used to adequately prevent recrudescence of symptoms in the setting of ITMIP. The related medication, nalbuphine, a partial opioid agonist has been found to be effective at treating ITMIP at the expense of increasing sedation and possibly nausea.²⁻⁵ Nausea and vomiting is a frequent complication during cesarean delivery.

After reviewing the literature, three investigations have evaluated promethazine for prophylactic or treatment of neuraxial morphine induced pruritus. First, Eldor and colleagues found intramuscular promethazine was effective at reducing the incidence and severity of pruritis induced by epidural morphine.⁶ Eldor conducted a randomized study among participants who had cesarean deliveries with epidural morphine. Those who received prophylactic IMP reported no pruritus while 35% of the control group experienced pruritus necessitating rescue treatment. Slappendel demonstrated that IMP was very effective at treating ITMIP.¹ Slappendel gave IMP to treat pruritus after varying doses of intrathecal morphine in orthopedic patients. Only one patient out of 143 subjects required escalation of therapy beyond IMP to treat ITMIP.¹ The article has not been confirmed nor refuted. This study was not blinded to the physician or the patient as this was their sole initial treatment for pruritus. Horta examined the potential of one of four different drugs to prevent ITMIP in patients undergoing cesarean delivery.⁷ In this randomized study, 300 women undergoing elective cesarean delivery were randomized to one of five groups (intravenous alizapride 100mg, propofol 20, droperidol 1.25mg, promethazine 50mg or saline control). Horta failed to find a prophylactic effect of intravenous promethazine to prevent ITMIP. We would like to study IMP in post-partum patients that have just undergone a cesarean delivery in a blinded study to see if this is an effective prophylaxis for pruritus. This would benefit the mother to not itch while also allowing the morphine to continue with pain relief.

[figure not shown]
In 2018, Vice O'Con et. al⁸ reviewed medications that were effective for treatment of post opioid pruritus and IM promethazine was not cited. They cited IV promethazine did not provide relief in this paper but could not find evidence for IM. Since very few medications actually work for this side effect, we would like to study IM promethazine in hopes to give another prophylaxis/treatment option that would not reverse the intrathecal narcotic. This paper cited that anti-dopaminergic medications did help decrease the pruritus but increased sedation in the forms given. Promethazine has a small amount of anti-dopaminergic activity and should decrease pruritus if it is truly a dopamine receptor mediated process.

5. **Specific Aims:** (research question/objectives)

Hypothesis: Prophylactic intramuscular promethazine does not decrease pruritus in post-partum females that received 100mcg intrathecal morphine.

Alternate Hypothesis: Prophylactic intramuscular promethazine does decrease pruritus in post-partum females that received 100mcg intrathecal morphine.

Pruritus will be quantified by the ItchyQuant Scale, developed and validated by CG Haydek as seen below.⁹

Secondary Analysis

- Promethazine does not increase sedation compared to placebo (RASS scale)
- Promethazine does not increase pain compared to placebo (DVPRS scale)
- Promethazine decreases nausea and vomiting (rated as none, mild, moderate, severe)

6. Research Plan:

Inclusion criteria:

1. Pregnant adult female patients of at least 18 years of age consenting to a cesarean birth;
2. Willing to consent to study.

Exclusion criteria:

1. Male patients;
2. Incarceration;
3. Inability to communicate with the investigators;
4. Allergies to any medications used in the study;
5. Possessing any contraindication to spinal anesthesia (lack of consent, elevated intracranial pressure, preexisting neurological disease, thrombocytopenia/coagulopathy, hypovolemia, infection at the site of the procedure);
6. Patients with an already prolonged QTc (>500 ms)
7. Any reason an investigator believes study participation would not be in the best interest of the potential subject.

DESIGN

STUDY PROCEDURES

Recruitment

Pregnant female patients already scheduled for a cesarean section operative procedure, as described in this protocol, will qualify for this study. The surgical schedule will be reviewed by the PI, [name], or one of the Co-I's, Drs., [name], [name], [name], or [name] as a part of their clinical duties. The PI and Co-I's are all Department of Anesthesiology staff and routinely work in the obstetrics unit, therefore, they all have a direct clinical relationship with the potential patients in this study. At least one of the PI or Co-I's will be working the obstetrics unit at the time of recruitment. Investigators (directly involved in clinical care) will review the surgical schedule and medical records of potential patients (as part of their routine clinical duties) greater than 1 day prior to surgery to more carefully evaluate the inclusion/exclusion for potential contraindications that could preclude or affect the patient's safety in the study. The extra step of oversight will help ensure potential patient safety prior to the surgeon approaching a patient to discuss the study.

Greater than 1 day prior to their scheduled surgery, all potential study participants identified as above will be contacted by phone and/or email if available by the PI or Co-I's. At this time, the PI or Co-I's will ask the patient if they are comfortable with a study coordinator contacting them and discussing a research study for which they qualify (phone script will be read). If the potential subject is interested, they will be provided the ICF. On the morning of surgery, additional questions and concerns will be addressed by one of the investigators (anesthesiologists) participating in the study and ICF will be completed. After obtaining written informed consent, women will be randomized into one of two groups: control or promethazine group. Method of randomization will be discussed below.

The hard copy consents will be stored in the study binder.

Patient typical day

The patient will come to the obstetric (OB) pre-operative holding area where we will obtain her medical history, perform a physical exam and consent her for the cesarean delivery. The patient will have already spoken with a study coordinator and/or PI/Co-I more than one day prior to arrival regarding potential participation in the study. The patient will be approached by one of the study team members (anesthesiologists). We will review the consent form, explaining that itching is a common side effect of the intrathecal morphine and we are trialing a medication that would prevent the itching. If the patient agrees to participate, we will obtain signed consent, contact the study coordinator to be prepared for questionnaires post-procedure and then obtain a blinded syringe from pharmacy for the treatment. [name] will randomize the patient for the study to determine which medication the mother will receive using a stratified randomization design generated with MAPLE software.

The patient will then go back to the operating room when it is her operative time, and we will perform the spinal with bupivacaine, morphine and fentanyl, which is standard at our institution (see standard of care medications below). Once the spinal is confirmed to be adequate, the surgical team will be called in to perform the procedure. Once the baby is delivered and the procedure is completed, we will inject the blinded syringe of medication into the patient's left thigh since she will still be numb from the spinal. When the patient arrives to the PACU, we will assess the 4 variables 1 hour after medication is given in PACU and then between 4-5 hours post-op and at 24 hours post-op (+/- 2 hours). All evaluations will be done in person or by phone call from study coordinator.

If patients are still reporting pruritis that is not controlled, the rescue treatment will be butorphanol 1mg IV q3h, as this is the current regimen at our institution.

Treatment/Therapy

The treatment will consist of a blinded syringe of 1cc clear liquid (blinded to patient and physician – only pharmacist will know what it contains). This injection will be given in the left thigh after the cesarean delivery is completed.

Contents of syringe: (either)

- 1cc 0.9% Sodium Chloride (placebo)
- 1cc 25mg/ml Promethazine (study medication)

Extra studies/procedures required

It is standard of care for all patients for this surgery to have intraoperative 5 lead EKG monitoring. All study patients will have QTc evaluated on the anesthesia monitor. As part of the study, rhythm strips will be printed out and saved in study binder. Any patients with an already prolonged QTc (>500 ms) will be excluded from the study.

Recording data responsibilities

1. Anesthesia attending on OB for the day will consent patient if they agree to the study.
2. [name] team will perform randomization.
3. Study coordinator will be contacted once patient is enrolled.
4. Time 0 will be recorded by resident/attending in the room at the time the medication is given.
5. Study coordinator will contact patient in person or by phone at 1 hour, 4-5 hours , and 24 (+/- 2 hours) hours to assess given variables.

Drugs that will be given as STANDARD OF CARE during the study will be:

1: Bupivacaine 0.75% 1.4-2.0 IT (Spinal anesthetic)

2: Fentanyl 20 mcg IT (Spinal anesthetic)

3: Preservative Free Morphine 100 mcg IT (Spinal anesthetic)

4: Butorphanol 1mg IV every 3 hours (rescue treatment)

5: Nalbuphine 2.5mg IV every 6 hours as needed for itching

6: Ondansetron 4mg IV every 6 hours as needed for nausea

7: Ketorolac 30mg IV once

8: Acetaminophen 975mg by mouth every 6 hours (scheduled)

9: Phenylephrine 100-200mcg as needed every 2 min and phenylephrine infusion 0.1 mcg/kg/min IV titrated to maintain maternal BP within 20% of baseline.

10: Ephedrine 5-10mg IV as needed every 2 min to maintain maternal BP within 20% of baseline, secondary agent to phenylephrine bolus and infusion and/or if maternal HR falls below 70 bpm.

11: Cefazolin 2g IV once before incision

12: Azithromycin 500mg IV once before incision

13: Clonidine 15-30mcg IT (Spinal anesthetic)

If penicillin allergic (given as STANDARD OF CARE):

1: Clindamycin 900mg IV once before incision

2: Gentamicin 1.5mg/kg IV once before incision

Drugs that will be given as part of the study:

1: Intramuscular Promethazine 25mg (25mg/mL)
2: Intramuscular 0.9% Sodium Chloride (placebo, also 1mL)

Table of Study Events

| Activity | Time Point | Time Point | Time Point | Time Point |
|--|------------|------------|------------|------------|
| Injection of blinded medication | 0 | | | |
| First Evaluation of variables (Phone call from coordinator) | | 1 h | | |
| Second Evaluation of variables (Phone call from coordinator) | | | 4-5 h | |
| Final Evaluation of variables (Phone call from coordinator) | | | | 24 h |

STATISTICAL METHODS, DATA ANALYSIS, AND INTERPRETATION:

Our plan is to recruit 50 patients for each arm of the study. With 50 patients on placebo and 50 patients on Phenergan, there will be a greater than 80% chance of detecting a significant difference of 20% or more at a two-sided 0.05 significance level. This assumes that severe itching occurs in 50% of patients and Phenergan reduces this proportion to 20%.

We will use Fisher's exact test to compare groups on severity of itching. We will also use Wilcoxon's rank sum test to compare groups on degree of itching as measured by the ITCHYQUANT. [name], the study biostatistician, will perform all statistical analyses.

DATA STORAGE AND DE-IDENTIFICATION PLANS:

The original, hard-copy signed informed consent forms and rhythm strips will be stored within the locked Anesthesiology research office and will remain with the Principal Investigator for at least 7 years. Data will be entered into an Excel spreadsheet kept on a password-protected and encrypted computer and retained by the Principal Investigator for at least 7 years.

Patients will be de-identified. No names, MRN's, or other identifying information will be stored in the spreadsheet. Pain, itching, sedation and nausea/vomiting will be collected at three intervals by a study coordinator and added to the de-identified spreadsheet. Age group, medical conditions such as diabetes and pre-eclampsia as well as BMI groups, will be used to determine confounders in the data. None of this collected information will be used to identify the patients.

7. Potential Risks:

Subjects will be given clear verbal and written instructions to contact [name] in the Department of Anesthesiology with questions or concerns regarding their study participation. If a patient experiences an injury that is directly caused by this study, they will receive professional medical care at the University of Florida. No other compensation is offered. Any adverse events will be reported to the

IRB using the standard adverse events reporting website and on continuing reviews (depending upon severity, as defined by the IRB).

1. Sedation (study variable). Promethazine can cause sedation which will be studied.
2. Concern for QT prolongation on the ECG causing cardiac arrhythmias. QTc evaluated on patient monitor, rhythm strip to be printed off and saved in research binder with QTc labeled clearly.
3. Respiratory depression
4. Painful injection site once spinal wears off. Patients will be given the injection while spinal anesthesia is still working to prevent pain during injection.
5. Tissue damage at site of injection
6. There is the risk of loss of confidentiality. The following procedures will be done to maintain confidentiality: written, paper forms will be kept in the locked Anesthesia Research Office. Computerized and de-identified records containing personal health information will be stored on password-protected and encrypted computers.

Routine medications that are provided to patients participating in the study may be provided to you. These are part of normal clinical care. The participant will be responsible for any deductible, co-insurance, or co-payments. Some insurance companies may not cover costs associated with research studies or research-related injuries. If the participant is injured as a direct result of participation in the study, only professional services received from any University of Florida Health Science Center healthcare provider (physicians, physician assistants, nurse practitioners, dentists or psychologists) will be provided without charge. Any other expenses, including Shands hospital expenses, will be billed to the subject's insurance provider or the subject themselves.

Safety Endpoint

During the study, we will log our adverse events. If the incidence for adverse events is greater than expected we will review the study design as a team to decide if we should proceed with the study or stop the study. If we have an increase incidence of serious injection site reactions, we will review whether the medication or placebo is causing the injection site reaction. If any major adverse reactions occur we will have a meeting with the investigators to address if this was an unanticipated or potentially expected event given the expected incidences.

8. Potential Benefits:

The potential benefit of this study would be to find a prophylactic treatment for intrathecal opioid pruritus. The patients would undergo minimal risk with an IM injection in attempts to decrease one of the major side effects of intrathecal opioids. The study will benefit future women undergoing cesarean section as we could give intrathecal morphine for post-op pain control with less side effects.

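### The pain aim compares DVPRS scores without recording opioid or other analgesic use, although opioids given for itch are likely to differ between arms

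*Combined protocol and SAP*

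**What the plan says.** The combined protocol and SAP, section 5 (Specific Aims, Secondary Analysis), states the aim as "Promethazine does not increase pain compared to placebo (DVPRS scale". No other pain measure is named.

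Section 6 sets the timing: "Study coordinator will contact patient in person or by phone at 1 hour, 4-5 hours , and 24 (+/- 2 hours) hours to assess given variables". Under the heading on the patient's typical day the first assessment is described as "we will assess the 4 variables 1 hour after medication is given in PACU". The data storage section identifies those variables: "Pain, itching, sedation and nausea/vomiting will be collected at three intervals by a study coordinator". It adds age group, medical conditions and BMI group as possible confounders. Drug use after the injection is not listed, either as an outcome or as a covariate.

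Two systemic opioids appear in section 6, both for itch. One is the rescue: "If patients are still reporting pruritis that is not controlled, the rescue treatment will be butorphanol 1mg IV q3h", repeated in the standard-of-care list as "Butorphanol 1mg IV every 3 hours (rescue treatment". The other is "Nalbuphine 2.5mg IV every 6 hours as needed for itching". The non-opioid analgesics in that list are ketorolac given once and acetaminophen on a fixed schedule. No as-needed drug for pain is listed.

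The statistical methods paragraph names Fisher's exact test and Wilcoxon's rank sum test, both for itch. It gives no test, margin or power for pain.

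**The concern.** A pain score taken after an opioid dose reflects both the pain and the dose. If the arms receive different amounts of opioid, equal DVPRS scores do not show equal pain, and unequal scores do not show that promethazine caused the difference. The plan creates this situation itself: it supplies opioids for the symptom that promethazine is meant to prevent, and does not list their use as data.

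The rationale in the background section is that itch can be relieved while the spinal morphine goes on working. The pain aim is the trial's check on that. As planned, the check rests on three spot scores with no record of which were taken soon after an opioid. Because the aim is a statement of no harm and has no planned test or margin, a null score comparison could be taken as support for it, whatever drugs lay behind the scores.

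**Working it through.** **1. The plan's own figure.** The only computed figure concerns itch: more than 80% power with 50 per arm for 50% versus 20% severe itching, two-sided 0.05. The normal approximation is Φ[(|p1 − p2| − 1.96·√(2·p̄·(1 − p̄)/n)) / √((p1(1 − p1) + p2(1 − p2))/n)]. With p̄ = 0.35 and n = 50 this is (0.30 − 1.96 × 0.0954)/0.0906 = 1.25, so power is 89.4%. Exact enumeration of Fisher's test gives 85.3%. The figure reproduces. What matters here is that the plan expects itch, the trigger for both listed systemic opioids, to differ by 30 percentage points.

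**2. The documented route: opioids given for itch.** Assume that every woman with severe itch, and no other, has received a rescue dose before a given DVPRS score. Expected numbers are 0.50 × 50 = 25 on placebo and 0.20 × 50 = 10 on promethazine. If a dose shifts a woman's score by k points, the difference in arm means shifts by (0.50 − 0.20) × k = 0.3k: 0.3, 0.6 and 0.9 points for k = 1, 2 and 3.

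The sign of k is open. If the rescue opioid relieves pain, placebo scores fall and promethazine looks worse. If it weakens the spinal morphine, placebo scores rise and promethazine looks better. The background section reports a suggestion that mu antagonists reduce analgesia, and describes nalbuphine as a related partial agonist, so the second sign cannot be excluded.

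For scale, the 95% confidence interval for a mean difference has half-width 1.96 × SD × √(2/50): 0.78, 0.98 and 1.18 points for assumed SDs of 2.0, 2.5 and 3.0. The documents give no DVPRS SD.

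**3. The undocumented route: analgesics given for pain.** This applies only if as-needed analgesics are used for pain, which the drug list does not show. Two illustrations follow, both on assumed inputs.

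(a) Suppose a true 1.5-point increase of which treatment removes a fixed fraction. Power of a two-sample t test, 50 per arm, two-sided 0.05:

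| Fraction removed | Difference left | SD 2.0 | SD 2.5 | SD 3.0 |
|---|---|---|---|---|
| none | 1.5 | 96% | 84% | 70% |
| a quarter | 1.125 | 80% | 61% | 46% |
| half | 0.75 | 46% | 32% | 24% |
| three quarters | 0.375 | 15% | 12% | 9.5% |

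The fraction removed is an input here, so the table shows a consequence of masking, not evidence that masking occurs.

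(b) Suppose instead that only scores of 5 or more are treated, each lowered by r points (simulated 0-10 scores, placebo mean 3.5, SD 2, 50 per arm, Wilcoxon test, 2,000 runs per setting):

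| True increase | r = 0 | r = 1 | r = 2 | r = 3 |
|---|---|---|---|---|
| 1 point: chance of detection | 67% | 66% | 55% | 31% |
| 1 point: mean difference left | 0.97 | 0.78 | 0.59 | 0.40 |
| 1.5 points: chance of detection | 95% | 94% | 87% | 57% |

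Mild treatment costs almost nothing; strong treatment costs a good deal. In no setting tried does the difference vanish. For the 1-point increase, 31% of placebo and 50% of promethazine women reach the treatment threshold. A record of analgesic use would show that contrast; the planned dataset would not.

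**The case against.** A reader might infer that a real increase in pain will be treated away with opioids and then reported as no increase. The documents do not support this. The standard-of-care list runs to 13 items, including antibiotics and vasopressors, and names as-needed drugs for itch and nausea but none for pain. Its non-opioid analgesics are fixed and do not rise with pain. That treatment follows pain in this setting is plausible, but it is not documented. The illustrations in step 3 also leave part of the difference in place. This objection stands: masking by pain treatment is a possibility of unknown size.

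A reader might also infer that the trial needs opioid counts to test the benefit in the abstract, "potentially decrease the use of systemic opioids in the initial post-operative period". That sentence ties the benefit to wider use of intrathecal narcotics. All women here are to receive the same intrathecal morphine dose, so the trial does not test it. This objection also stands.

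Finally, unequal rescue use presupposes that promethazine works, and the background section cites a randomised study in which the intravenous form did not prevent itch. That is fair. But a 30-point difference is the plan's own design assumption, so the pain aim should be able to cope with it. If rescue use turns out equal, only a record can show that.

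None of these objections touches the gap itself: DVPRS is the only pain measure, and no analgesic or rescue use is listed as collected.

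**Conclusion.** The point holds in a limited form. The pain aim compares spot scores under opioid exposure that is unrecorded and, on the plan's own expectations, unequal. The direction of any bias is not known from the documents. Its size is 0.3 points per point of rescue effect if rescue use matches the assumed severe-itch rates exactly; that match and the rescue effect are both assumptions. Masking by as-needed pain treatment is a further possibility that rests on care the protocol does not list, and the power losses shown for it are illustrative only.

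This concerns one of three secondary aims. The primary itch analysis is not affected by this point. It is a cheap improvement that changes what the pain aim can conclude.

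**What to change.** - **Collect.** At the 24 h contact, extract from the medication record every systemic opioid and as-needed analgesic dose from Time 0 to 24 h, with drug, time and indication. Add these items to the data storage section.
- **Report.** Show pain-indicated and itch-indicated use separately by arm, beside DVPRS, with between-arm differences and confidence intervals. Flag each DVPRS score taken after a rescue dose.
- **Conclude.** State in the statistical methods section that the pain conclusion will be worded from the DVPRS confidence interval together with the comparison of analgesic use. A non-significant or numerically equal score should not suffice alone. Nor should a rule that neither measure be higher on promethazine: without a margin, a harmless drug would often fail it by chance if it is read numerically, and if it is read as not significantly higher it treats lack of evidence as evidence of no harm.
- **Clarify.** Say in the standard-of-care list whether as-needed systemic analgesics for pain are part of usual care. This asks for a description only, not for a change in care.

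The cost is one chart extract per patient, a few sentences in the plan and a more cautious pain statement. No visits, staff or patients are added.

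### Randomisation is stratified but both itch tests are pooled: the tests stay valid, and following the strata would give a small, conditional gain in power

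*Combined protocol and SAP*

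**What the plan says.** - **Allocation.** Section 6, Recruitment, announces: "Method of randomization will be discussed below". The only description that follows is under Patient typical day, where the woman is randomised "using a stratified randomization design generated with MAPLE software". No stratification factor, number of strata or block size is given there or later.
- **Outcome.** Section 5, Specific Aims: "Pruritus will be quantified by the ItchyQuant Scale".
- **Tests.** Section 6, Statistical Methods, plans Fisher's "exact test to compare groups on severity of itching" and Wilcoxon's "rank sum test to compare groups on degree of itching as measured by the ITCHYQUANT". Neither is linked to the strata.
- **Size and power.** The same section: "Our plan is to recruit 50 patients for each arm of the study", with the claim that "there will be a greater than 80% chance of detecting a significant difference of 20% or more at a two-sided 0.05 significance level". The rates behind it: "This assumes that severe itching occurs in 50% of patients and Phenergan reduces this proportion to 20" per cent.
- **Covariates.** The data storage section says that age group, conditions such as diabetes and pre-eclampsia, and BMI groups will be looked at as confounders. It does not call them strata and names no adjusted or stratified test.

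**The concern.** Stratifying forces the arms to be alike on factors thought to matter. A pooled test ignores that balance. Its reference distribution still allows for chance differences between arms that the design has removed, so its true false-positive rate falls below the nominal level and some power is left unused. A test that compares arms within strata recovers it. With 100 women and no stated allowance for dropout, power that needs no extra patients is worth having. How much there is depends on how strongly the strata predict itch, which the protocol does not say.

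**Working it through.** **Inputs.** From Statistical Methods: 50 per arm, two-sided 0.05, severe itch 50% v 20%. The power sentence speaks of a difference of 20% or more, whereas its rates differ by 30 points. That mismatch is a separate matter; the stated rates are used here. Assumed, because the documents are silent: two strata of equal size, exactly 25 per arm in each, a common treatment odds ratio, and overall rates held at 50% and 20%.

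**Step 1: the plan's own figure.** Power of pooled Fisher is the sum, over all pairs (x, y) with Fisher p ≤ 0.05, of Bin(x; 50, 0.5) × Bin(y; 50, 0.2). Full enumeration gives 85.3%, so the claim of more than 80% is reproduced at these rates.

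**Step 2: prognostic strata.** If the placebo rates are a and 1 − a, the stratum odds ratio is ((1 − a)/a)². For 30%/70% this is (0.7/0.3)² = 5.44. The treatment odds ratio is then chosen so that the promethazine rates average 20%. With 4.95, the placebo odds 0.429 and 2.333 become 0.087 and 0.471, which are rates of 8% and 32%, mean 20%.

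**Step 3: like with like.** The exact stratified test adds the promethazine events over strata and refers the total to its exact distribution given each stratum's margins. Both tests are exact and conditional, so the difference comes from stratification alone. All entries are full enumerations.

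| Placebo rates by stratum | Stratum odds ratio | Pooled Fisher power | Exact stratified power | Gain (points) | Null size, pooled / stratified |
|---|---|---|---|---|---|
| 50/50 | 1 | 85.27% | 85.32% | 0.05 | 3.52 / 3.52% |
| 44.9/55.1 | 1.5 | 85.36% | 85.56% | 0.2 | 3.43 / 3.43% |
| 41.4/58.6 | 2 | 85.54% | 86.09% | 0.5 | 3.25 / 3.28% |
| 35/65 | 3.45 | 86.12% | 87.97% | 1.9 | 2.72 / 3.05% |
| 30/70 | 5.44 | 86.80% | 89.94% | 3.1 | 2.15 / 3.09% |

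The gain keeps growing: 4.4 points at 25/75 and 5.6 at 20/80. With a 90/10 split of patients between strata it is smaller: 0.4, 1.0 and 1.7 points at odds ratios 2, 3.45 and 5.44. Simulations with 4, 8 and 16 strata at a similar spread gave similar gains to two strata.

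**Step 4: in patients.** Pooled Fisher at 51 per arm has 86.43% power at odds ratio 1.5 and 86.65% at 2, already above the stratified 85.56% and 86.09% at 50 per arm. Mild strata are thus worth under one patient per arm. At 3.45, pooled Fisher gives 87.76% at 52 and 89.45% at 54, against 87.97%: two to three. At 5.44 it gives 90.16% at 54, against 89.94%: about four. Beyond that the equivalent is larger.

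**Step 5: ItchyQuant, illustration only.** Assumed: scores of 0 to 10, total SD 2.5, effect 1.5 points, two equal strata, 40,000 simulated trials per case.

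| Stratum shift (points) | Pooled Wilcoxon power | Van Elteren power | Null size, pooled |
|---|---|---|---|
| 0 | 82.3% | 82.0% | 5.1% |
| 1 | 82.4% | 83.0% | 4.5% |
| 2 | 83.9% | 87.9% | 3.2% |
| 3 | 85.9% | 94.7% | 1.3% |

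Nothing in the documents supports any particular shift.

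**Step 6: cost if the strata do not predict itch.** The exact stratified test lost at most 0.2 points, even with 16 strata. Van Elteren lost about 0.2 to 0.5 points with 2 strata, about 1 with 4 to 5, and 2 to 2.5 with 8 to 10. The aligned rank test lost about 0.1 with 5 or 10.

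**Step 7: why not uncorrected Cochran-Mantel-Haenszel.** In simulation at 30/70, Fisher gave 86.8%, Pearson chi-square 91.0% and uncorrected CMH 93.3%. Of the 6.5-point rise, 91.0 − 86.8 = 4.2 comes from dropping Fisher's conservatism and only 93.3 − 91.0 = 2.3 from stratifying. With useless strata the swap still adds about 4 points. Its null size ran from 4.7 to 6.0%.

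**The case against.** The strongest reply is that nothing is broken. The pooled tests control false positives, the power target is met without stratification, and the size of the gain rests on assumed strata. It may be zero, and the scheme may have no strata at all. All of that stands, and it is why the point is minor.

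Two further objections stand in part. First, exact balance within strata is an assumption, since the protocol mentions no blocking. In a simulation of 20,000 trials at 30/70 without blocking inside strata, pooled Fisher's null size was about 4.2% rather than 2.15%, and power was 86.6% v 90.9%. The pooled test is then less conservative, but the gain does not vanish. Second, a stratified analysis is not free in every form: van Elteren loses power when there are many uninformative strata. The aligned rank test meets that.

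It could also be said that the listed covariates (age, diabetes, pre-eclampsia, BMI) already cover the matter. They do not: the protocol treats them as possible confounders, not as the randomisation strata, and attaches no test to them.

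**Conclusion.** The mismatch is real: stratified allocation, strata not named, and only pooled tests planned. It is a minor matter of efficiency. For severe itch, under two equal balanced strata and a common odds ratio, the gain runs from about 0 to 3.1 points for strata up to 30/70, worth from under one to about four patients per arm. That range is not a ceiling. The arithmetic for severe itch is firm given those assumptions; the prognostic strength of the strata is unknown, and the ItchyQuant figures only show that the gain there could be larger.

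A reader might infer that pooled tests after stratified randomisation are invalid, or that the trial misses its power. The documents do not support either. The error of the pooled tests is on the conservative side when balanced strata predict itch, and power at 50% v 20% is at least 85.3% in every enumerated case.

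**What to change.** In Statistical Methods, before unblinding:

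1. Name the strata of the MAPLE scheme.
2. Make the exact stratified (conditional) test the test for severe itch. Do not treat uncorrected CMH as its equivalent.
3. Make a stratified rank test the test for ItchyQuant: van Elteren if the strata are few, the aligned rank test (Hodges-Lehmann) if there are about five or more small ones.
4. Keep pooled Fisher and Wilcoxon as sensitivity analyses.
5. If the scheme has no strata, delete the word *stratified* and keep the pooled tests.

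The cost is a few sentences and, if it is not already there, one coded stratum column in the de-identified spreadsheet. No patients or procedures are added. The statistical downside is essentially nil for the exact stratified test, and about 0.1 point for the aligned rank test when the strata are uninformative.
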